7.1.2.1 Efficacy Analysis Set 1 (EFS1)

All patients in Cohort 1 who received [⁶⁸Ga]FAPI-46, with an interpretable (when answer to eCRF question: “Is Image of technical quality for interpretation?” is “Yes”) FAPI-46 PET image result (positive or negative) for at least 1 lesion with a corresponding histopathology result (positive or negative).

All patients in Cohort 2 who received [⁶⁸Ga]FAPI-46, with an interpretable FAPI-46 PET image result for at least 1 lesion with a corresponding histopathology result. For patients with multiple PET scans, only one PET scan will be considered for analysis. The most recent PET scan performed prior to surgery for patients with multiple scans will take precedence for analysis.

7.1.2.2 Efficacy Analysis Set 2 (EFS2)

All patients in Cohort 1 who received [⁶⁸Ga]FAPI-46, with interpretable FAPI-46 PET image results (positive or negative) for at least 1 lesion with corresponding IHC results (positive or negative).

All patients in Cohort 2 who received [⁶⁸Ga]FAPI-46, with interpretable FAPI-46 PET image results for at least 1 lesion with corresponding IHC results. For patients with multiple PET scans,

only one PET scan will be considered for the main analysis. The most recent PET scan performed prior to surgery for patients with multiple scans will take precedence for analysis.

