
Duration of Participation
	
Unless otherwise specified, ‘days,’ refers to calendar days. Study day 1 refers to the day the (first) [⁶⁸Ga]FAPI-46 PET occurs, day 2 is the following calendar day, etc.
 
Cohort 1 Participants receiving surgical intervention, not prescribed neoadjuvant therapy by their oncology team:
 
 • Screening period (≤ 28 days from study day 1) • Standard of care diagnostic modality: MR, CT and/or [¹⁸F]-FDG PET • Day 1: [⁶⁸Ga]FAPI-46 PET radiopharmaceutical administration, scan and safety assessment • +24 to 72 hours post-injection of [⁶⁸Ga]FAPI-46: safety follow up assessment • Surgical intervention ≤21 days of [⁶⁸Ga]FAPI-46 PET scan • Tissue samples from surgical intervention assessed for FAP expression 
Cohort 2 Participants who are candidates to receive surgical intervention, prescribed neoadjuvant therapy by their oncology team prior to surgery
 
 • Screening period (≤ 28 days from study day 1) • Standard of care diagnostic modality: MRI, CT and/or [¹⁸F]-FDG PET • Day 1: [⁶⁸Ga]FAPI-46 PET radiopharmaceutical administration, scan 1 and safety assessment • +24 to 72 hours post-injection of [⁶⁸Ga]FAPI-46: safety follow up assessment • Neoadjuvant therapy as prescribed by the oncology team. Core biopsy must be obtained prior to initiation of neoadjuvant therapy • ≤ 21 days of surgery: [⁶⁸Ga]FAPI-46, radiopharmaceutical administration, scan 2 and safety assessment • +24 to 72 hours post-injection of [⁶⁸Ga]FAPI-46: safety follow up assessment • ≤ 21 days of surgery: Standard of care diagnostic modality: MR, CT and/or [¹⁸F]-FDG PET • Surgical intervention as per institutional standard and oncology team direction 
Tissue samples from biopsy and surgical intervention assessed for FAP expression

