6.1.2 Justification of Sample Size

The sample size is 60 patients in order to adequately power the primary objective of sensitivity.

For this study, the primary efficacy endpoints is sensitivity, evaluated with a hypothesis test:

H0: Sensitivity \leq PG

H1: Sensitivity $>$ PG

The minimum sample size necessary to achieve power for sensitivity was computed for the hypothesis test above utilizing a one-sample binomial proportion test with a normal approximation, an upper one-sided significance level of 0.05, and the following parametric assumptions:

- PG = 0.75 for sensitivity
- True Sensitivity = 0.90

Given the parametric assumptions above, 60 patients yields 92.7% power to demonstrate that the true sensitivity is greater than 0.75.

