6.2.1 Primary Efficacy Measures

The primary efficacy endpoints will be defined based on a [⁶⁸Ga]FAPI-46 PET image result (positive or negative) and a histopathology result (positive and negative) at patient level. Imaging data reads were conducted by a single reader at a central image reading lab followed by quantitative recording of PET image SUV data. The primary tumor and up to a maximum of three lymph nodes were assessed by the central lab and only those lesions that have both imaging and histopathology results will be used for primary endpoint calculation.

For the primary analysis, sensitivity will be determined based on a single tissue sample from biopsied or resected specimens collected from the primary tumor

Refer to [Table 10](#) to determine positive imaging and histopathology results.

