- g IHC will be performed for FAP expression at a central lab on biopsy tissue; Histopathology for the detection of pancreatic cancer is performed locally
- h Passive follow-up only through chart review to collect information about post-surgical imaging, planned treatment, and outcomes for 14 days following surgery.
- i AE assessments will be performed 24 hours post [⁶⁸Ga]FAPI-46 injection
- j Follow up visits may be performed through televisits. Patients may utilize institution approved local labs/mobile clinics for blood draws as part of follow up assessment
- k Standard of care imaging post NAT Cycle 1 and prior to surgery. If multiple Standard of care images are taken post-surgery, the one closest to the surgery date will be used for image analysis
- l Labs obtained during screening period, within 72 hours of Day 1, can be used as pre-FAPI-46 injection Day1 lab data.

Note: days are counted as calendar days unless otherwise specified. The day before study day 1 is Day -1.

Source: Protocol GaFAP-2022P2 Version 5.0, 31st March 2023

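### For Cohort 2 the SAP fixes the post-treatment scan but not the tissue it is compared with, so scan and specimen may be paired across neoadjuvant therapy

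*SAP*

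**What the plan says.** - **Scan.** SAP 7.1.2.2 (EFFS2, used for the correlation): "The most recent PET scan performed prior to surgery for patients with multiple scans will take precedence for analysis". SAP 7.1.2.1 (EFFS1, used for the primary analysis) and 10.6 give the same rule. In Cohort 2 the second scan follows NAT and precedes surgery by at most 21 days.
- **Tissue for the primary endpoint.** SAP 6.2.1 rests sensitivity on "a single tissue sample from biopsied or resected specimens collected from the primary tumor". It does not say which to take when both exist. Table 10 labels the histopathology parameter as biopsy.
- **Tissue for IHC.** Footnote g to the Cohort 2 schedule, in protocol 1.3 and SAP Appendix 1: "IHC will be performed for FAP expression at a central lab on biopsy tissue". The footnote is attached to the surgical resection row.
- **Timing of the biopsy.** Protocol 1.1, Cohort 2: "Core biopsy must be obtained prior to initiation of neoadjuvant therapy". The same entry says that biopsy and surgical tissue are both assessed for FAP.
- **Design text.** Protocol 1.1 and 6.1 and SAP 6.1 describe comparison of the scans with resected tumour.
- **Correspondence.** SAP 10.6.2 explains a corresponding histopathology result as one from the same lesion. It says nothing about the same period.
- **Missing truth standard.** SAP 7.1.2 and 9.4 count missing or invalid histopathology as positive, because every patient entered with confirmed PDAC.
- **Pooling.** SAP 10.6 presents efficacy for both cohorts combined. SAP section 8, which lists changes from the protocol, does not mention the pairing.

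**The concern.** The scan rule is definite and the tissue rule is open. Someone programming from SAP 6.2.1, Table 10 and footnote g could set a post-NAT scan against a pre-NAT biopsy without breaking any stated rule. NAT may change both tumour and stroma, and an exploratory objective of the trial is to look for such change.

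Three results are exposed:

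- **The SUVmax–H-score correlation on EFFS2.** This is the most exposed, because footnote g names biopsy tissue. Treatment change between specimen and scan would weaken the correlation for reasons unrelated to the tracer. The exploratory IHC-based sensitivity and specificity share the problem.
- **The pooled primary sensitivity.** A patient with no residual tumour is still positive by the old biopsy. A negative scan 2 is then a false negative. A positive scan 2 is a true positive, although the protocol itself notes that FAP is also expressed in inflammation and fibrosis.
- **Patients with scan 2 but no valid resection result.** The impute-positive rule sets their entry diagnosis against a post-NAT scan, with the same effect.

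**Working it through.** **1. The plan's own figure.** Inputs from SAP 6.1.2: "an upper one-sided significance level of 0.05", "PG = 0.75 for sensitivity", "True Sensitivity = 0.90", and the stated result "60 patients yields 92.7% power to demonstrate that the true sensitivity is greater than 0.75".

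Test statistic: z = (r/n − 0.75) / √(0.75 × 0.25 / n), compared with 1.645. For n = 60 the standard error is √(0.1875/60) = 0.0559. Then 50/60 gives z = 1.491 and 51/60 gives z = 1.789, so the test succeeds at 51 or more. The exact binomial power of that rule at 0.90 is 92.69%, with a size of 4.52%. The stated 92.7% is reproduced. It does not depend on the pairing rule.

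**2. Primary analysis, four patients without residual tumour (assumed).** The other 56 patients have tumour in the tissue used. On resected tissue the four leave the sensitivity denominator. On the old biopsy, or by imputation, they stay in it as positives. The counts among the 56 are also assumed.

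| Scan 2 in the four | Tissue | Count | z | One-sided p |
|---|---|---|---|---|
| Negative | Resected | 48/56 = 85.7% | 0.1071/0.0579 = 1.85 | 0.032 |
| Negative | Pre-NAT biopsy | 48/60 = 80.0% | 0.0500/0.0559 = 0.89 | 0.19 |
| Positive | Resected | 47/56 = 83.9% | 0.0893/0.0579 = 1.54 | 0.061 |
| Positive | Pre-NAT biopsy | 51/60 = 85.0% | 0.1000/0.0559 = 1.79 | 0.037 |

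The choice of tissue changes the conclusion in both cases, in opposite directions.

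**3. Power when those patients are negative on scan 2.** Let f be the Cohort 2 share of the 60 and x the share of Cohort 2 without residual tumour. The documents give neither; the ranges assumed are f = 0.25 to 0.75 and x = 0.05 to 0.20. Against the old biopsy, pooled sensitivity is 0.90 × (1 − f·x).

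| f | x | Sensitivity | Power, old biopsy | Power, resected tissue (n) |
|---|---|---|---|---|
| 0.25 | 0.05 | 0.889 | 87.5% | 93.3% (59) |
| 0.50 | 0.10 | 0.855 | 63.0% | 88.8% (57) |
| 0.75 | 0.20 | 0.765 | 7.6% | 86.7% (51) |

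**4. Correlation.** Assumptions: same-period correlation 0.6; pre- and post-NAT H-scores correlate at q = 0.2 to 0.8; every Cohort 2 pair crosses NAT; no mean shift. The pooled linear correlation is then 0.6 × [(1 − f) + f·q]. This runs from 0.6 × (0.75 + 0.20) = 0.57 (f = 0.25, q = 0.8) to 0.6 × (0.25 + 0.15) = 0.24 (f = 0.75, q = 0.2). The planned statistic is Spearman's. Simulation (400,000 draws, bivariate normal) gives about 0.58 for matched pairs, against:

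- f = 0.25: 0.46 to 0.55
- f = 0.50: 0.35 to 0.52
- f = 0.75: 0.24 to 0.49

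The model ignores that SUV is reported only for regions read as positive, so lesions negative on scan 2 have no SUV to correlate.

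**The case against.** The best defence is that the intended comparator is the surgical specimen. The design text in both documents says so, and choosing the scan nearest surgery makes most sense with a surgical comparator. Footnote g hangs on the resection row, so its reference to biopsy tissue may be loose wording for resected tissue. The choice of biopsied or resected tissue in SAP 6.2.1 may be there for Cohort 2 patients who never reach a second scan or surgery. For them, scan 1 with the biopsy is a same-period pair. On this reading little or nothing crosses NAT.

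Much of this stands:

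- A reader might infer that the SAP prescribes post-NAT scans against pre-NAT biopsies, or that the correlation is certain to be weakened. The documents support neither; they permit the mismatch and do not require it.
- A reader might infer that a separate Cohort 2 sensitivity is at risk. None is planned; Cohort 2 enters only the pooled estimate.
- The scan rule bites only on patients with two scans.
- The numerical examples are scenarios, and the primary ones lie close to the 51/60 cut-off.

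What does not stand is that the text settles the matter. SAP 6.2.1, Table 10 and footnote g point towards biopsy tissue, or allow it, while SAP 6.1 points to resected tissue. Nor can the error be assumed to run only towards lower sensitivity: the positive-scan rows show the opposite.

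**Conclusion.** The point holds as a gap in the pairing rule, with conflicting text around it. For Cohort 2 patients with two scans, the scan is post-NAT and the specimen may be pre-NAT. The pooled Spearman correlation is the most exposed result. The pooled primary sensitivity is affected only through patients whose tumour status at surgery differs from that at entry, including those scored by imputation.

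The size cannot be fixed from the documents, which give no Cohort 2 share, no rate of absent residual tumour, and no correlation of H-score across NAT. On the assumed ranges the loss runs from minor (correlation 0.58 to 0.55, power 87.5%) to severe (correlation 0.24, power 7.6%). Four patients can be enough to reverse the primary conclusion either way. If only resected tissue is used with scan 2, and nothing is imputed, the problem disappears.

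This should be fixed before analysis. Confidence is moderate, because the sponsor may already intend the matched pairing.

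**What to change.** In SAP 6.2.1, 7.1.2.1, 7.1.2.2 and 10.6:

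1. Require same-period pairs, stated separately for histopathology and IHC. Use scan 2 with the resected specimen where both exist, otherwise scan 1 with the pre-NAT biopsy, and never pair across NAT. This also covers a Cohort 2 patient who has surgery with only scan 1 available.
2. Reconcile 6.2.1, Table 10 and footnote g with the comparison to resected tissue in 6.1. Say which specimen footnote g means.
3. In 7.1.2 and 9.4, do not impute positive histopathology from the entry diagnosis against a post-NAT scan. Use scan 1 with the biopsy for those patients.
4. Show sensitivity and the Spearman correlation by cohort beside the pooled result.

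The cost is SAP wording and some programming. Both scans and both tissues are already planned, so no new procedure is needed. The documents do not confirm that specimen type and date are in the database, so this should be checked first. A few patients may be analysed on scan 1 or drop out of EFFS2.

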7.1.2.3 Efficacy Analysis Set 3 (EFFS3)

All patients from Cohort 1 and Cohort 2 who received [⁶⁸Ga]FAPI-46, have interpretable FAPI-46 PET and standard of care images (ie, CT or MRI or [¹⁸F]-FDG PET).

7.1.2.4 Efficacy Analysis Set 4 (EFFS4)

All patients in Cohort 2 who received [⁶⁸Ga]FAPI-46, with interpretable FAPI-46 PET image results prior to NAT and post NAT for the same lesion.

7.1.3 Per Protocol Analysis Set (PPS)

All patients in the EFFS1 who completed the study according to the protocol with no critical protocol deviations. The decisions regarding critical protocol deviations, and the definition of the analysis set, will be finalized prior to database lock.

7.2 Subgroups

Not applicable.

8 CHANGES IN CONDUCT OR PLANNED ANALYSES FROM THE PROTOCOL

Per protocol, the primary efficacy endpoint compares the results from [⁶⁸Ga]FAPI-46 PET and histopathology and potential metastases were to be assessed as follows:

“[⁶⁸Ga]FAPI-46 PET/CT will be analyzed for lesions that are visually considered as suggestive of metastases based on the morphology, focality and intensity of [⁶⁸Ga]FAPI-46 uptake. Lesions will be counted, classified with respect to their locations (liver, peritoneum, non-regional lymph nodes, lung, bone, and other), and their [⁶⁸Ga]FAPI-46 avidity will be semi-quantitatively analyzed through SUV_{max}.”

During the blinded read of the [⁶⁸Ga]FAPI-46 PET, the reader assessed the pancreas as well as a maximum of 3 lymph nodes and recorded the SUV for lesions judged positive. The exact location of the lymph nodes assessed, while some are available in the DICOM RT structures, is not recorded in the database. Consequently, the comparison with histopathology results can only be done for the primary pancreatic lesion.

Protocol	SAP	Description
Primary Efficacy Endpoint: Sensitivity, specificity, and accuracy determined on a per-lesion basis for all lesions with tissue available for analysis	Primary Efficacy Endpoint: Sensitivity to detect PDAC determined on a per-patient basis using histopathology as standard of truth	Histopathology result and Blinded read assessment are both available for the primary pancreatic lesion only. Besides, per inclusion criteria, subjects were included with a confirmed PDAC. Consequently, only per-subject sensitivity can be assessed for the primary endpoint.
Exploratory Efficacy endpoints: Number of malignant lesions (local, metastatic) identified through anatomical (i.e, CT, MR) and/or [18F]-FDG PET Number of [⁶⁸ Ga]FAPI-46 identified lesions and the radiotracer accumulation observed in local and metastatic disease using SUV	Number of lesions identified (0, 1, 2, 3 or more) through Standard of Care (anatomical (ie, CT, MRI) and/or [18F]-FDG PET) and [⁶⁸ Ga]FAPI-46 PET images Radiotracer accumulation observed in identified lesions using SUV	With both Standard of Care and [⁶⁸ Ga]FAPI-46 PET images, the reader recorded uptake values observed in the pancreas and a maximum of 3 lymph nodes judged positive. Consequently, the detection of metastatic disease cannot be compared.
Exploratory Efficacy endpoints: Percentage change in [⁶⁸ Ga] FAPI-46 PET imaging using SUV levels and number of identified	Percentage change in [⁶⁸ Ga]FAPI-46 PET imaging using SUV levels in the primary lesion between pre- and post-neoadjuvant therapy	Given the lack of correspondence in the regions of interest between the pre- and post-NAT PET scans, changes in SUV between Visit 1 and Visit 3 can only be observed for the primary lesion

lesions between pre- and post-neoadjuvant therapy		
The primary analysis of sensitivity and specificity will be summarized using frequency counts and percentages as well as 95% asymptotic normal confidence intervals.	The point estimate, SE, as well as the 90% asymptotic normal CI will be presented for sensitivity. The 95% asymptotic normal CI will also be presented; however, the primary focus will be on the 90% CI to align with the 5% one-sided test.	The primary focus will be on the 90% CI to align with the 5% one-sided test; however, the 95% asymptotic normal confidence interval will also be presented.

9 OVERALL STATISTICAL CONSIDERATIONS

9.1 General Conventions

Statistical testing for sensitivity will be one-sided and performed at the 0.05 level.

Summary statistics will be presented for categorical data as number and percentage (n [%]) where the percentage is displayed to 1 decimal point (eg, 98.1).

Descriptive statistics will be presented for continuous data with applicable decimal precision as follows in relation to the source data (indicated as N + x), with a maximum of 3 decimals to be displayed:

Number, (n).

Mean, (N + 1).

Standard deviation (SD), (N + 2).

Median, Q1, Q3, (N + 1).

Minimum, (N + 0).

Maximum, (N + 0).

9.2 Multiple Comparisons and Adjustment for Multiplicity

No alpha adjustment is required for statistical testing in this Phase 2 study. The type I error rate will be preserved by requiring the rejection of the sensitivity null hypothesis to conclude that [⁶⁸Ga]FAPI-46 is effective for the detecting PDAC.

9.3 Baseline Definition

Baseline for a given parameter is defined as the last non-missing evaluation before the first dose of [⁶⁸Ga]FAPI-46 for Cohort 1 and 2.

In addition, given NAT in Cohort 2 and [⁶⁸Ga]FAPI-46 are excreted from the body after 10 half-lives (\pm 10 hours), assessments after NAT and the last non-missing evaluation before the second dose of [⁶⁸Ga]FAPI-46 will be considered as post-NAT Baseline. Also, a pre- and post- NAT evaluation will be considered to evaluate the change in assessments before and after NAT and will be described in each relative section. Any assessment between the first dose of [⁶⁸Ga]FAPI-46 and NAT will be considered as post study treatment. Summaries will clearly indicate the difference between change from baseline (CFB) (if applicable) and change from pre-NAT.

9.4 Imputation and Handling of Partial Dates

Patients with missing or invalid histopathology data (the standard of truth) will be considered positive for the primary region of interest, in line with the study design, which requires all

patients to be positive for PDAC in order to be eligible for inclusion. Missing SUV values for the primary tumor, where the response in the EDC is interpretable (i.e., ‘Yes’ to the eCRF question: ‘Is the image of technical quality for interpretation?’), will be treated as a region considered negative by the blinded reader. Otherwise, no imputation for missing data will be performed unless explicitly specified. Rules for partial and missing dates for AEs and medications are given in the [Appendices](#).

9.5 Interim Analysis

No formal interim analysis is planned for this study.

9.6 Pooling Strategy for Study Sites

Patient data will be reported under the site recorded into the EDC database and then pooled for analysis purposes.

9.7 Visit Windows / Unscheduled Visits

The study date and corresponding study visits will be captured on each eCRF. Safety analyses will use the nominal visits as collected in the study database, thereby, visit windows will not be applied.

Unscheduled visits will not be included in by-visit summaries or analyses but may contribute to the baseline, last pre-NAT (Cohort 2 only), worst post baseline, and worst post-NAT (Cohort 2 only) assessments.

The following visit convention will be used for by-visit efficacy TLFs. Refer to [Section 6.1](#) for an extensive description of each visit.

Table 3. Visit Windows

Cohort	Visit Description/Window	Visit Format within TLFs
Cohort 1	≤ 28 days of day 1	Screening*
	Study day 1	Visit 1*
	+ 24 to 72 hours post-injection	Visit 2
	≤ 21 days of PET scan	Surgery
	14 days following surgery	Surveillance
	Any unscheduled visit	Unscheduled
	End of study assessments	End of Study
Cohort 2	≤ 28 days of day 1	Screening*
	Study day 1	Visit 1*
	+ 24 to 72 hours post-injection (1 st)	Visit 2
	Post Neo-adjuvant Treatment Monitoring	NAT
	≤ 21 days of surgery	Visit 3*
	+ 24 to 72 hours post-injection (2 nd)	Visit 4
	≤ 21 days of PET scan	Surgery
	14 days following surgery	Surveillance
	Any unscheduled visit	Unscheduled
	End of study assessments	End of Study

Abbreviations: NAT = neoadjuvant therapy; PET = positron emission tomography; TLFs = table, listing, and figure's

*Depending on the assessment, if considered a baseline value at that visit then the visit will be renamed to Baseline for statistical summaries.

10 STATISTICAL ANALYSIS METHODS

10.1 Patient Disposition

All screened patients who provided informed consent will be accounted for in the study. The number of patients in the following disposition categories will be summarized in a summary table by cohort and overall:

- The number of patients screened, enrolled, and completed the study
- The number of patients in each analysis population
- Patients who discontinued prematurely, reasons for study discontinuation (possible options are progressive disease, AEs, death, protocol deviation, physician decision, sponsor request, withdrawal by patient, lost to follow-up, study terminated by sponsor, patient non-compliance, or other).

The following listings will be presented:

- Screen Failures: A list of all screen failures, including the date of informed consent, reason for failure, and the associated inclusion/exclusion violation number.
- Inclusion/Exclusion Violations: A list of all inclusion/exclusion violations.
- Disposition: A list indicating the first and second dose dates, Cohort 2 patients who underwent NAT, date of study completion or discontinuation, and reason for discontinuation for all enrolled patients.
- Exclusion from Analysis: A list of reasons for exclusion from the analysis populations for all enrolled patients.

